Research has shown that a successful implementation depends on interplay between the effectiveness of the implementation strategies chosen to support the implementation and characteristics of the implementation object, the implementers, the target population and the context of the implementation (Table 1).

Updated design of the implementation research

The project was planned to be conducted using a cross-over design in two counties in south of Sweden based on a feasibility/pilot study that was conducted during fall 2014 *co-created palliative care educational intervention through seminars for professionals in nursing homes*. Due to a more significant amount of drop-outs compared with expected (and for not receiving the total amount of applied foundation), the plan needed to be revised. The knowledge-based palliative care intervention was conducted as a non-randomized control trial, implemented over a six-month period in 30 nursing homes in two different counties in the south of Sweden (County A and County B). The data collection was made in two sequential periods in each county. First, the intervention was implemented in ten nursing homes in County A (Kronoberg County from April 2015), while ten nursing homes in County B served as a control group. Then, County B implemented the intervention (Skåne county from August 2016), and ten new nursing homes in County A, which had not received the intervention, were chosen as a control group. After the two sequential time periods were data from one intervention and one control group analysed. The selection through voluntary participation resulted in a mixture of both larger and smaller nursing homes within the two counties (cluster samples), as well as both from urban and rural areas.

Implementation object

According to the National Board of Health and Welfare, palliative care should be based on four cornerstones: symptoms relief, multi-professional cooperation, communication and relation as well as support to the next of kin (Socialstyrelsen 2012). The aim of palliative care is to reduce suffering and promote the quality of life for patients with progressive, incurable illnesses or injuries. The care should address physical, psychosocial and spiritual needs as well as provide support to the next of kin. The definition by the National Board of Health and Welfare closely

adheres to the definition of palliative care by the World Health Organization (WHO), (Socialstyrelsen 2013).

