Sub study 5: Staff	Focus group interviews (preparedness for implementation)	20 staff divided into 3 groups before and after the implementation is finished	
Sub study 6: Staff	Questionnaires at two occasions: Experiences of palliative care (46 items), P-CAT (13 items) and the Person-Centered Climate Questionnaire (14 items)	100 staff before and after the implementation is finished	100 staff with 6 months in between
Sub study 7: Managers	Two individual interviews with managers (organic preparedness for implementation)	20 managers at different levels-, during the intervention and after six months	
Sub study 8: Implementation context	An ethnographic study: Observations and qualitative interviews	Observations on 28 occasions at 7 nursing homes with a strategic selection of qualitative interviews during the implementation	

THE OVERALL AND SPECIFIC AIMS

The overall aim of this research project is to evaluate the outcomes and effectiveness of the implementation method of a knowledge-based model for palliative care in nursing homes. The overall aim can be broken down into four specific research questions and nine different studies:

1. What is the outcome of the implementation intervention in terms of quality of life, participation and quality of care in older persons and next of kin at nursing homes before and after? (Study I, II-IV)
2. Investigates the staff's implementation process of palliative care and the role of the leadership and (Study V-IX).
3. Investigate which factors (barriers and facilitators) that affect the implementation process of this model (Study V, VII-IX).

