Official title of the study:
Implementation of Knowledge-Based Palliative
Care for Frail Older Persons in Nursing Homes

NCT number: NCT02708498

Date of the document: April 8, 2015, updated October 6, 2020

Statistical Analysis Plan

Simple descriptive statistics:

Median-Mean, Quartiles, Percentage

These are applied to all quantitative studies.

Baseline study:

Target population: Older people

Instruments: Characteristics of older participants, WHOQOL-BREF & WHOQOL-OLD

The data were analysed in one descriptive and one analytical section. In the descriptive section, numbers and percentages were calculated on a group level. A mean score was calculated for each domain using both the raw domain score, a standardized domain score (SDS) with the raw domain score divided by the number of items in the domain (1-5) and a transformed domain mean score (TDS 0-100) according to the instrument manuals. The different calculations were performed to enable comparison of our results with those from other studies.

In the analytical section, the participants were divided into two age groups (66-88 years and 89-102 years) by the population median age and gender (female and male). To examine differences in quality of life, a comparison of medians was conducted using the Mann-Whitney U test.

Comparative studies (Baseline and Follow-up):

Target population: Older people, next-of-kin, staff

Instruments: PCAT, PCQ-S, PCQ-P, WHOQOL-BREF, WHOQOL-OLD, Your experience of palliative care, Next-of-Kin Participation in Care (NoK-PIC)

The selection of the statistical tests to analyze data other than the descriptive statistics was based on whether the data were distributed normally and the scale level of the instruments. The Mann-Whitney U-test and the Kruskal-Wallis test was applied to compare the baseline characteristics of the two groups. The quantitative data collected from questionnaires were analyzed using within-group comparisons (the data from after the intervention period were compared with the data from before the intervention period in the intervention group and the control group) by Wilcoxon signed rank test.

Either Pearson's chi-square test or Fisher's exact test was used when the expected value was less than 5.

A two-tailed p-value of <0.05 was regarded as statistically significant.

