In order to investigate if the drop-outs consisted a threaten of external validity we performed sub-groups analysis through comparing the drop-outs in the intervention group with the participants in the intervention group, and comparing the drop-outs within the control group with the participants in the control group.

Analyses were performed using IBM SPSS Statistics version 24.

Logistic regression studies (Baseline and Follow-up):

Target population: Staff
Instruments: P-CAT, PCQ-S

A univariate logistic regression analysis was performed with the independent variable improvement/non-improvement in P-CAT and PCQ-S and the dependent variable group (control/implementation).

Psychometric studies

Target population: Next-of-kin
Instrument: Next-of-Kin Participation in Care (NoK-PiC)

Step 1. Dimensionality

The dimensionality of the 37 items was explored by means of Rasch Model Analysis (RMA) and Explorative Factor Analysis (EFA). EFA needs complete data, i.e. no missing responses in any items. RMA can process missing data. Estimation methods merely summarize the non-missing observations that are relevant, and compare them with their expectations.

NoK-PiC data was analysed according to Rasch Measurement Theory (RMT), using the polythomous Rasch model in RUMM2030 (Professional Edition 5.4). A principal component analysis of the residuals was conducted in RUMM2030 to explore dimensionality of the NoK-PiC items. Person location estimates were derived from subsets of items that loaded positively and negatively on the first principal component of residuals. The overall proportion of persons with significantly different measures from the two item subsets should be <5% to support unidimensionality.

EFA was conducted based on recommendations including parallel analysis to decide for decision about how many factors to retain for rotation, Minimum Rank Factor Analysis (MRFA, that is able to estimate the percentage of common variance explained by the EFA model), and on a promine rotation that allows factors to correlate (oblique). In addition, since the items are polythomous, and since MRFA assume only minor departures from normality, we based the analysis on a polychoric correlation matrix. The software FACTOR (Lorenzo-Seva, Ferrando, release 10.5.03, June 2017) was used to conduct EFA.

Step 2. Item reduction

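### The only explicit between-arm follow-up test of the staff P-CAT and PCQ-S scores ignores clustering by nursing home, so its standard errors are somewhat too narrow

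*SAP*

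**What the plan says.** The SAP section on logistic regression studies gives the staff analysis in one sentence: "A univariate logistic regression analysis was performed" "with the independent variable improvement/non-improvement in P-CAT and PCQ-S and the dependent variable group (control/implementation". It names no term for home, county or period and no robust variance. Neither document defines improvement.

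No other test in the SAP is explicitly a between-arm comparison of these scores at follow-up:

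- Comparative studies section: "The quantitative data collected from questionnaires were analyzed using within-group comparisons", by Wilcoxon signed rank test. Mann-Whitney and Kruskal-Wallis are assigned to baseline characteristics. The chi-square/Fisher sentence is tied to no outcome.
- Drop-out comparisons are made within each arm.
- Step 5 of the psychometric section uses Mann-Whitney tests between independent groups of next of kin and does not call those groups trial arms.

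The protocol's section on the updated design describes "smaller nursing homes within the two counties (cluster samples), as well as both from urban and rural areas". In the first period ten County A homes received the intervention, "while ten nursing homes in County B served as a control group". In the second period County B received the intervention and "ten new nursing homes in County A, which had not received the intervention, were chosen as a control group". Table 2, Sub study 6, plans 100 staff in the implementation homes and, for the controls, "100 staff with 6 months in between".

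**The concern.** Staff in one home share a manager, a seminar group and a workplace, so their score changes may be correlated. A model that treats them as independent overstates the information in the data: its confidence interval is too narrow and its p-value too small. The County B homes add a second dependence. The protocol counts 30 homes, and 10 (County A, intervention) + 10 (County B) + 10 (new County A, control) = 30 only if the same County B homes serve first as controls and then as intervention homes.

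At stake is any statement, resting on this model, that staff P-CAT or PCQ-S scores improved more in the intervention arm. The Wilcoxon tests cannot supply one, because they do not compare arms.

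**Working it through.** The plan states no ICC, SD, effect size or power, so it has no figure to reproduce. The following is illustration under stated assumptions.

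**Inputs from the documents.** Two-sided 5% level (SAP). Four cells of 10 homes: County A intervention and County B control in period 1; County B intervention and new County A control in period 2. That is 30 homes, 40 home-periods and 20 home-periods per arm. If Table 2's 100 staff is the arm total, m = 100/20 = 5 staff per home-period. If it is per arm and period, m = 200/20 = 10.

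**Assumptions.** Normal change scores; improvement means any rise above 0; ICC of the change score ρ = 0.02, 0.05 or 0.10; home effects either persist across periods or are independent by period.

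**Step 1: reference without clustering.** Enumerating both binomial counts gives the exact size of the Wald logistic test. With 100 per arm it is 5.6% if half of staff improve (mean change 0) and 5.0% if 61.8% do (mean change 0.3 SD). With 200 per arm it is 5.1% and 4.9%.

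**Step 2: closed form at mean change 0.** Cutting at the median turns ρ into an ICC of the yes/no indicator, ρb = (2/π)·arcsin(ρ) = 0.0127, 0.0318, 0.0638. The variance inflation is

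- independent by period: DE = 1 + (m − 1)ρb
- persistent: DE = 1 + (m/2 − 1)ρb, because shared County B effects cancel between arms

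and the actual level is 2[1 − Φ(1.96/√DE)]. Example: m = 10, ρ = 0.10, independent: DE = 1 + 9 × 0.0638 = 1.574, level 11.8%.

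**Step 3: simulation of the same layout** (100,000 trials per setting, no true effect):

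| m | Home effects | Closed form, ρ = 0.02 / 0.05 / 0.10 | Simulated, mean change 0 | Simulated, mean change 0.3 SD |
|---|---|---|---|---|
| 5 | persistent | 5.2 / 5.6 / 6.1% | 5.8 / 6.2 / 6.8% | 5.2 / 5.5 / 6.1% |
| 5 | independent | 5.6 / 6.5 / 8.0% | 6.2 / 7.1 / 8.8% | 5.6 / 6.4 / 8.0% |
| 10 | persistent | 5.6 / 6.5 / 8.0% | 5.6 / 6.5 / 8.2% | 5.5 / 6.4 / 7.8% |
| 10 | independent | 6.3 / 8.4 / 11.8% | 6.6 / 8.5 / 12.2% | 6.2 / 8.2 / 11.7% |

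The two agree once the 0.6-point discreteness at 100 per arm and mean change 0 is allowed for.

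**Step 4: the part due to clustering.** With m = 5 the excess over Step 1 runs from 5.8 − 5.6 = 0.2 points to 8.8 − 5.6 = 3.2 points. With m = 10 it reaches 12.2 − 5.1 = 7.1 points, which needs ρ = 0.10 and independent home effects together.

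**Step 5: does accounting for home repair it?** Cluster-robust errors by home with a small-sample correction (24 degrees of freedom, county and period as covariates) rejected in 4.8-5.2% of null trials. A random home intercept fitted to home-period means gave 4.9-6.0%.

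**Step 6: what it cannot repair.** Intervention occupies the cells (A, period 1) and (B, period 2); control occupies (B, period 1) and (A, period 2). Group is therefore the county-by-period interaction. If the counties' trends differ by 0.3 SD and there is no intervention effect, the planned test rejects in 41% of trials, the cluster-robust comparison of change scores in 48% and the mixed model in 50%.

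**The case against.** The strongest reply is that the harm is small. Part of the excess at mean change 0 is discreteness of the test, the top figure needs several unfavourable assumptions at once, and no ICC is documented. This stands, and the size claimed here allows for it. Applying the usual design effect with the assumed ICC taken directly as that of the yes/no outcome gives up to 15.5% (m = 10, ICC 0.10: DE = 1.90). That takes no account of the cut or of County B effects cancelling, and the documents give no basis for an ICC that high.

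Four stronger readings are tempting, and the documents do not support them:

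- **Every claim about staff improvement rests on this test.** Staff also complete the palliative-care experience questionnaire, which this model does not cover, and the chi-square/Fisher sentence could refer to arms.
- **The unstated cut invalidates the result or was chosen after seeing the data.** Any rise is a natural reading, and nothing shows a later choice. In simulation with a 0.4 SD effect, cuts at 0 and 0.5 SD gave different verdicts in about 25% of trials, but the planned test and a cluster-robust change score also disagreed in 22%. This is missing detail that one sentence supplies.
- **Cutting the score necessarily costs power.** With 5 staff per home-period and a 0.4 SD effect, normal scores give 60-62% as planned against 63-77% for the clustered uncut change. With t (5 df) scores the difference vanishes (75-78% against 73-78%). With Laplace scores it reverses (83-89% against 73-78%). The SAP chooses tests "based on whether the data were distributed normally and the scale level of the instruments", and the score tests it names are rank-based, so normality cannot be presumed.
- **Reversing outcome and group spoils the estimate.** With 62/100 against 47/100 improved, OR = (62 × 53)/(38 × 47) = 1.84, 95% CI 1.05-3.23, p = 0.034 in either direction. The roles need correcting for interpretation, and because a home effect cannot sensibly be added with group as the outcome.

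**Conclusion.** The concern holds, with modest size. The SAP's one explicit between-arm follow-up test of staff P-CAT and PCQ-S treats staff as independent in a study allocated by home, so its standard errors are somewhat too narrow. Under assumed ICCs of 0.02-0.10, a nominal 5% test rejects in about 5-9% of null trials with 5 staff per home-period and about 5-12% with 10, against about 5-5.6% without clustering. These figures rest on normal change scores, a cut at any rise, equal cell sizes and the same County B homes in both arms. The omission itself needs none of these assumptions.

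The scope is two staff scales under the second aim. The point does not touch the quality-of-life and participation outcomes of older persons and next of kin, and correcting it does not remove confounding by differential county trend. The change should be made.

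**What to change.** 1. Make improvement the dependent variable and group the independent variable, and state the cut that was used, including how unchanged scores are classed.
2. Account for clustering by home with a small-sample correction suited to about 30 homes, for example cluster-robust errors by home, with the County B homes kept as the same clusters in both periods.
3. As a sensitivity analysis labelled post hoc, compare the uncut score change between arms with a clustered method chosen after the distribution check that the SAP already describes, rank-based if scores are heavy-tailed. Before the re-run, state which estimate decides, so that the addition does not create a new choice.
4. Report as a limitation that group coincides with the county-by-period interaction, so none of these analyses removes a differential county trend.

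The cost is SAP wording and a small re-run on scores already collected, provided each staff record can be linked to home, county and period. If it cannot, the cut can still be stated and the clustering reported as a limitation. Intervals will be wider, and the responder test loses power: 49-57% instead of 60-62% for a 0.4 SD effect with normal scores and 5 staff per home-period. The uncut score brings no assured gain in power.

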The Person-centered Care Assessment Tool (P-CAT) measures the extent to which an aged care setting is person-centered. The tool is primarily intended for use by staff but expanded with a version for the older person's self-reporting. The Swedish version of the P-CAT has been found to be valid, reliable, and applicable for further use (Edvardsson *et al.* 2010, Sjögren *et al.* 2012). Person-centered care is increasingly regarded as being synonymous with best quality care. In this project, both the staff version and the version for the older will be used.

The Person-Centered Climate Questionnaire: The Person-centered Climate Questionnaire exists both in a patient and a staff version. The instruments have been shown as being a valid and reliable contribution for assessing to what extent the climate of care environments is person-centered. The factors are safety, everydayness and hospitality. The instrument enables descriptions and comparisons of environments, exploration of correlates between person-centeredness and patient outcomes and/or measure results of various interventions (Bergland *et al.* 2015, Edvardsson *et al.* 2013).

The newly developed self-reported questionnaire was named Next of Kin Participation in Care (NoK-PiC): Before the start of this project, there was a complete lack of instruments designed to measure the participation of next of kin in palliative care in nursing homes. To deal with this, a questionnaire for next of kin's participation was developed before the beginning of the project. Literature reviews of previous research about the next of kin's participation was performed including all types of care in general as well as focus on palliative care and the care at nursing homes. The systematic literature review resulted in a questionnaire with 36 items about next of kin's participation in palliative care. The new questionnaire was psychometrical tested on 400 next of kin (Westergren et al. 2020).

Experiences of palliative care: The staff will also answer a questionnaire with 47 items, newly constructed to capture changes in health professionals' attitudes, knowledge and assessment of the quality of palliative care; before (one month's), and after finishing the implementation intervention. Validation of the questionnaire is ongoing (Östlund et al. 2014).

Focus group interviews and individual interviews

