Based on conceptual reasoning among the researchers and based on RMA item reduction was conducted. The main statistical reasons for item reduction was based on item fit. In general, individual item fit residuals should range between -2.5 and 2.5, with the ideal being 0. Signs of multidimensionality/under discriminating items (fit residuals >2.5) and local dependency/item redundancy/over discriminating items (fit residuals > -2.5) led to further exploration of the possible reasons for misfit. This exploration included inspection of item residual correlations, and the item characteristic curves to get a graphical understanding of the deviations from Rasch model expectations. The nature of observed misfit (local response dependence or multidimensionality) often needs to be determined based on conceptual reasoning rather than statistics.

Step 3. Dimensionality after item reduction

Dimensionality of the remaining 30 items (after step 2) was explored using EFA, following the same procedures as described above (Step 1). The appropriateness of performing EFA was, in this step, checked according to quality criteria, i.e. by means of: the Kaiser-Meyer-Olkin Measure of Sampling Adequacy (should be KMO 0.50 or above); and Bartlett's test (should be p-value <0.05).

Step 4. RMA of final and separate factors

According to RMA, a set of items, supposed to be unidimensional, rated (dichotomous or polytomous scoring) in a sample, are compared to the "Perfect Rasch Model" that is based on fundamental measurement principles from the physical sciences. The model separately locates persons and items on a common interval level logit metric, ranging from minus to plus infinity, with mean location set at zero. The extent to which a successful measurement has been achieved is determined by examining the fit between observed data and model expectations. If data accord sufficiently with the model, linear measurement and invariant comparisons are possible. However, almost no scale is perfect, thus "almost perfect" can be a goal to achieve. Here the RMA addresses targeting, reliability, model fit, Differential Item Functioning (DIF, by gender and age), and hierarchical item ordering.

Step 5. Group comparisons

The IBM SPSS Statistics 23 software was used for comparisons between independent groups. Data were assessed regarding underpinning assumptions, described, and analysed using Mann Whitney U-tests. Significance was set to $P < 0.05$.

Target population: Next-of-kin

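### The <5% rule for NoK-PiC unidimensionality is applied to an item split chosen from the same responses, so a share of 5% or more is not by itself evidence against a single dimension

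*SAP*

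**What the plan says.** The SAP, Psychometric studies, Step 1 (Dimensionality) examines the 37 NoK-PiC items with a polytomous Rasch analysis and an exploratory factor analysis (EFA). On the Rasch side: "A principal component analysis of the residuals was conducted in RUMM2030 to explore dimensionality of the NoK-PiC items". The subsets follow from that component: "Person location estimates were derived from subsets of items that loaded positively and negatively on the first principal component of residuals". The criterion is: "The overall proportion of persons with significantly different measures from the two item subsets should be <5% to support unidimensionality".

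Step 1 gives no minimum loading, hold-out sample, confidence interval for the share or simulated reference value. It does not state the level of the person-level test. The only general statement, "A two-tailed p-value of <0.05 was regarded as statistically significant", stands under Comparative studies.

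On sample size, the Protocol (Methods and instruments, NoK-PiC) says: "The new questionnaire was psychometrical tested on 400 next of kin". The SAP gives no number of respondents for Step 1.

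In the same step, parallel analysis within the EFA decides how many factors to retain. Step 2 removes items on conceptual grounds and item fit. Step 3 rechecks the remaining 30 items by EFA. Step 4 runs the Rasch analysis on the resulting factors and does not list the residual-component test again.

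**The concern.** The 5% benchmark comes from the person-level test: if two subsets measure the same thing and were fixed beforehand, about 5% of persons will differ at the two-sided 5% level by chance. The first residual component is the largest shared contrast among the items in this sample, noise included. Splitting by its signs puts items whose residuals happen to move together on the same side. Testing those same persons on that split therefore raises the expected share above 5% with no second dimension present.

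This differs from sampling error around 5%. The expectation itself moves, so a confidence interval around the observed share does not repair it. What is at stake is how a share of 5% or more is read. Taken at face value, it would be reported as evidence that NoK-PiC is not one scale, when a perfect single scale would usually give the same result.

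**Working it through.** The SAP gives a criterion, not a derived figure, so there is nothing to reproduce. The check asks what the rule does when unidimensionality is true.

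**Inputs**
- Items: 37 (SAP, Step 1). The Protocol says 36; both were run.
- Respondents: 400 (Protocol); 100 to 5000 also run.
- Split: all items by sign of loading (SAP, as the text reads).
- Person test: two-sided 5%, |t| > 1.96 (assumed).
- Response categories: 4 (assumed); 5 also run.
- Main setting: item locations SD 1, persons N(0, 1), weighted-likelihood person estimates.

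**Steps for each simulated data set**
1. Generate responses from an exactly unidimensional partial credit model.
2. Compute standardised residuals and take their first principal component.
3. Split items by sign of loading and estimate each person from each subset.
4. t = (estimate₊ − estimate₋) / √(se₊² + se₋²).
5. Share = number of persons with |t| > 1.96, divided by n. The rule fails if the share is 5% or more.

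**Results, one true dimension (4 categories and n=400 unless stated)**

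| Setting | Mean share | Rule failed |
|---|---|---|
| Sign split | 9.3% (5th–95th percentile 8.0–11.0%) | 200 of 200 |
| Sign split, n=200 | 11.4% | 100% |
| Sign split, n=100 | 15.2% | 100% |
| Sign split, n=1000 | 7.3% | 100% |
| Sign split, n=5000 | 5.8% | 40 of 40 |
| 5 categories | 9.2% | 100% |
| 36 items | 9.1% | 100% |
| Maximum-likelihood person estimates | 9.6% | 100% |
| Item parameters estimated | 9.3% | 15 of 15 |
| Persons 2 logits off target | 7.7% | 99.5% |
| Persons 3 logits off target (SD 1.5) | 6.1% | 85% |
| Random split fixed in advance | 4.5% | 35% |

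For 400 respondents the cut-off is 0.05 × 400 = 20 persons. The expected count under one dimension is 0.093 × 400 ≈ 37.

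Separate simulations of the n=400 sign split gave means of 8.3%, 8.6%, 8.7% and 9.0%, with no data set passing. With off-target persons, other runs gave 5.9–6.6%, and in two of them 8% and 15% passed.

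**Isolating the cause.** Choosing the split in one random half of respondents and testing in the other brought the mean share back to about 4–5%. The model and test are unchanged, so the excess comes from choosing and testing on the same persons.

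**Separating sampling error.** If the true person-level rate is exactly 5%, the chance of 20 or more of 400 is 0.53 (exact binomial). So a bare point rule is unstable even with a fixed split. If failure instead requires the lower 95% limit to exceed 5%, a fixed split fails in 1.5% of samples but the sign split still fails in 98.5%.

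**Effect of a minimum absolute loading (not in the SAP)**

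| Limit | n | Mean share | Rule failed |
|---|---|---|---|
| 0.2 | 400 | 8.5% | 100% |
| 0.3 | 400 | 4.1% | 27% |
| 0.3 | 250 | 5.5% | 60% |
| 0.3 | 200 | 6.6% | 72% |

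The 0.3 rows count only data sets that left enough items on each side. Two other runs with that limit at n=400 had 89% and 95% of such data sets passing.

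**Does the share still discriminate?** With the sign split at n=400, one run gave 8.6% for one dimension (5th–95th percentile 6.5–10.0%). Two dimensions correlated 0.9 gave 21% (18.0–24.5%), correlated 0.8 gave 32%, and correlated 0.6 gave 45%.

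**The case against.** **The text does not say that every item was assigned.** It speaks of items loading positively and negatively and sets no limit either way. If only items above about 0.3 were used, most of the inflation at n=400 disappears. This stands: the near-certain failure is conditional on assignment by sign. But the SAP states no limit, a limit of 0.2 does not help, and 0.3 does not suffice at n=200–250.

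**The share is not worthless.** A reader might infer that the test carries no information. The simulations show otherwise: even two dimensions correlated 0.9 are clearly separated from one. The bias also runs in one direction, so a share below 5% would still support unidimensionality.

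**No decision hangs on the test.** A reader might infer that the rule forces NoK-PiC to be split and so alters a trial outcome. The documents do not show this. Parallel analysis sets the number of factors, Step 2 uses item fit and conceptual reasoning, and Step 3 uses EFA alone. Nothing says that a share of 5% or more leads to splitting, and the SAP does not say which NoK-PiC score enters the before–after comparisons. This objection stands in full and limits the consequence to how Step 1 is interpreted.

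**The work appears to be done.** The SAP is in the past tense and already gives 30 remaining items. That affects how the fix is delivered, not whether the cut-off is valid.

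**Conclusion.** The <5% cut-off is miscalibrated for the procedure described. With all 37 items assigned by sign and 400 respondents, a truly unidimensional polytomous scale has an expected share of about 8–9%, or about 6–8% with persons 2 logits off target, and fails the rule in about 85–100% of samples. The inflation is larger with fewer respondents. A value of 5% or more is therefore not evidence of multidimensionality, while a value well above the simulated range would be.

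The result rests on assignment by sign without a minimum loading, a two-sided 5% person test, and 4 or 5 response categories. The Protocol's 400 is taken as the analysed number. The documents do not support a claim that the test is uninformative, that it determined the final scoring, or that it changes any comparison between groups.

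**What to change.** 1. **State the procedure.** Say whether all items were assigned by sign or only those above a stated loading. Give the level of the person test, the number of response categories and the number of respondents analysed.

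2. **Replace the cut-off.** Suggested wording: Data sets will be simulated from the fitted Rasch model with the same respondents, items and missing-data pattern; the residual component, item split and person tests will be repeated in each; unidimensionality will be questioned only if the observed share exceeds the 95th percentile of the simulated shares. About 1000 data sets would do. With 4 categories and the sign split, that percentile is about 10–11% at n=400 and about 14% at n=200. By construction, a true single scale is then wrongly questioned about 5% of the time. The simulated shares for two dimensions correlated 0.9 (18.0–24.5% at n=400) still lie above the limit.

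3. **Alternative.** Choose the split in a random half of respondents and test it in the other half. This halves the persons tested (400 to 200). It should be judged by whether the lower 95% limit exceeds 5%: with a pre-fixed split at n=200, the bare <5% rule failed a true single scale in 42.5% of samples, against 0.5% for the lower-limit rule.

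4. **If Step 1 has already been run,** leave the description of what was done, report the recalibrated reference beside the result, and do not read a share between 5% and the simulated limit as evidence against one dimension.

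The cost is a few sentences and some computing time; no new data are needed.
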